7.2. Participant Discontinuation/Withdrawal From the Study

A participant will be withdrawn from the study for any of the following reasons:

- The participant discontinues study intervention (see Section 7.1)
- Esketamine nasal spray becomes accessible in an individual's local country
- Lost to follow-up
- Withdrawal of consent
- Death

When a participant withdraws before study completion, the reason for withdrawal is to be documented in the eCRF and in the source document. If the reason for withdrawal from the study is withdrawal of consent then no additional assessments are allowed.

Refer to Section 4.4 for study completion definition for participants.

Withdrawal of Consent

If a participant is unable to return for scheduled visits, it does not necessarily constitute withdrawal of consent. Alternate follow-up mechanisms that the participant agreed to when signing the consent form apply, as local regulations permit.

7.3. Lost to Follow-up

A participant will be considered lost to follow-up if he or she repeatedly fails to return for scheduled visits and is unable to be contacted by the study site. A participant cannot be deemed

lost to follow-up until all reasonable efforts made by the study-site personnel to contact the participant are deemed futile. The following actions must be taken if a participant fails to return to the study site for a required study visit:

- The study-site personnel must attempt to contact the participant to reschedule the missed visit as soon as possible, to counsel the participant on the importance of maintaining the assigned visit schedule, to ascertain whether the participant wishes to or should continue in the study.
- Before a participant is deemed lost to follow up, the investigator or designee must make every reasonable effort to regain contact with the participant (where possible, 3 telephone calls, e-mails, fax, and, if necessary, a certified letter to the participant's last known mailing address, or local equivalent methods. These contact attempts should be documented in the participant's medical records.
- Should the participant continue to be unreachable, they will be considered to have withdrawn from the study.

Should a study site close, eg, for operational, financial, or other reasons, and the investigator cannot reach the participant to inform them, their contact information will be transferred to another study site.

8. STUDY ASSESSMENTS AND PROCEDURES

Overview

The Schedule of Activities (Section 1.2) summarizes the frequency and timing of efficacy and safety measurements applicable to this study.

Visit-specific PRO assessments should be conducted/completed before clinician-rated assessments, any tests, procedures, other consultations, or administration of esketamine nasal spray to prevent influencing participant perceptions. Refer to the PRO completion guidelines for instructions on the administration of PROs.

All clinician-rated scales must be completed prior to administration of esketamine nasal spray.

Actual dates of PRO and clinician-rated assessments will be recorded in the source documentation and eCRF.

Urine pregnancy tests (at site/local) will be performed in accordance with the Schedule of Activities (Section 1.2) and Section 8.2.4, Pregnancy Testing. Counseling on pregnancy prevention will be provided at all visits, when applicable.

The total blood volume to be collected from each participant will be approximately 30 mL (approximately 7-8 mL/visit), which may vary based on length of participation and local laboratory requirements. Repeat or unscheduled samples may be taken for safety reasons or for technical issues with the samples.

Sample Collection and Handling

The actual dates of sample collection must be recorded in the eCRF.

Refer to the Schedule of Activities (Section 1.2) for the timing and frequency of all sample collections.

Study-Specific Materials

The investigator will be provided with the following supplies:

- Investigator's Brochure for esketamine
- Investigational Product Binder, including the investigational product procedures manual
- Instructions for use documents (participant and healthcare provider versions) for esketamine nasal spray
- Instructions for product quality complaint (PQC) reporting requirements
- Paper versions of PRO questionnaires and PRO completion guidelines
- Paper versions of clinician-administered assessments (MADRS, C-SSRS)
- Rater qualifications/requirements for select clinician-administered assessments
- Electronic devices and associated materials, as applicable
- IWRS Manual
- Sample ICF
- Independent Ethics Committee (IEC)/Institutional Review Board (IRB) approved participant materials

8.1. Efficacy Assessments

The sponsor will use the clinician-rated scales and PROs from Week 32 in Study TRD3013 in the database for Day 1 in this long-term extension study; these procedures do not need to be repeated for participants who return for esketamine nasal spray dosing within 14 days after the Week 32 visit in TRD3013.

8.1.1. Clinician-Rated

At all scheduled visits indicated in the Schedule of Activities, all clinician-rated scales must be completed prior to administration of esketamine nasal spray.

8.1.1.1. Montgomery-Asberg Depression Rating Scale (MADRS)

The MADRS is a clinician-rated scale designed to measure depression severity and detect changes due to AD treatment (Montgomery 1979). The scale consists of 10 items, each of which is scored from 0 (item not present or normal) to 6 (severe or continuous presence of the symptoms), for a total possible score of 60. Higher scores represent a more severe condition. The MADRS evaluates apparent sadness, reported sadness, inner tension, sleep, appetite, concentration, lassitude, inability to feel (interest level), pessimistic thoughts, and suicidal thoughts. The test exhibits high interrater reliability. The MADRS will be administered at the time points specified in the Schedule of Activities.

Rating of the MADRS will be conducted face-to-face with the participants by the rater. The rater should have sufficient qualifications as documented by experience or training prior to being assigned as rater. To avoid interrater variability, all efforts should be made to have the same independent rater rating the same study participants as much as possible. If possible, for individual participants, the independent rater from Study TRD3013 may continue performing the MADRS in this study. The MADRS takes about 30 minutes to complete.

In case of worsening of depressive symptoms and MADRS increase to \geq 22, an additional assessment should be performed within the next 5 to 31 days to confirm the relapse criteria. The date of the second MADRS assessment will be used for the date of relapse.

The secondary efficacy endpoint, as described in Section 3, uses the MADRS (total score) as part of the criteria for relapse.

8.1.1.2. Clinical Global Impression – Severity (CGI-S)

The CGI-S is an observer-rated scale that measures illness severity (Guy 1976). The CGI-S has proved to be a robust measure of efficacy in many clinical drug trials and is easy and quick to administer. The CGI-S is rated on a 7-point scale, with the severity of illness scale using a range of responses from 1 (normal) through to 7 (among the most severely ill participants). The CGI-S takes about 15 minutes to complete.

8.1.2. Patient-Reported Outcomes

Patient-reported outcomes will be completed by the participants at the timepoints indicated in the Schedule of Activities. As previously noted, all PRO assessments must be conducted/completed before clinician-rated assessments, any tests, procedures, other consultations, or administration of esketamine nasal spray.

The PRO assessments should be performed in the order as listed in the subsections below and in the Schedules of Activities in Section 1.3.

- The PRO instruments will be provided in the local language in accordance with local guidelines.
- The PRO instruments must be available for regulators and for IRB/IEC submissions, therefore the PRO instruments are attached to the protocol in Appendix 7.
- The PRO and AE data will not be reconciled with one another.

8.1.2.1. Patient Health Questionnaire, 9-Item (PHQ-9)

The PHQ-9 is a validated 9-item, PRO measure to assess depressive symptoms (Spitzer 1999). The scale scores each of the 9-symptom domains of the DSM-5 MDD criteria and it has been used both as a screening tool and a measure of response to treatment for depression. Each item is rated on a 4-point scale (0=not at all, 1=several days, 2=more than half the days, and 3=nearly every day). The participant's item responses are summed to provide a total score (range of 0 to 27), with higher scores indicating greater severity of depressive symptoms. The PHQ-9 takes about 5 minutes to complete.

European Quality of Life (EuroQol) Group, 5-Dimension, 5-Level 8.1.2.2. (EQ5D-5L)

The EQ-5D-5L is a validated standardized instrument for use as a measure of health outcome, primarily designed for self-completion by respondents (EuroQol Group n.d.; EuroQol Research Foundation 2009). It consists of the EQ-5D-5L descriptive system and a visual analogue scale (EQ-VAS). The EQ-5D-5L descriptive system comprises the following 5 dimensions: Mobility, self-care, usual activities, pain/discomfort, and anxiety/depression. Each of the 5 dimensions is divided into 5 levels of perceived problems (Level 1 indicating no problem, Level 2 indicating slight problems, Level 3 indicating moderate problems, Level 4 indicating severe problems, and Level 5 indicating extreme problems).

The participant selects an answer for each of the 5 dimensions considering the response that best matches his or her health "today". The descriptive system can be represented as a health state. The EQ-VAS self-rating records the respondent's own assessment of his or her overall health status at the time of completion, on a scale of 0 ("The worst health you can imagine") to 100 ("The best health you can imagine"). The time taken to complete the questionnaire varies with age, health status, and setting but is likely to be around 5 minutes.

8.2. **Safety Assessments**

Adverse events will be reported and followed by the investigator as specified in Section 8.3, Adverse Events, Serious Adverse Events, and Other Safety Reporting, and Appendix 5, Adverse Events, Serious Adverse Events, Product Quality Complaints, and Other Safety Reporting: Definitions and Procedures for Recording, Evaluating, Follow-Up, and Reporting.

Any clinically relevant changes occurring during the study must be recorded on the Adverse Event section of the eCRF.

Any clinically significant abnormalities persisting at the end of the study/early withdrawal will be followed by the investigator until resolution or until a clinically stable condition is reached.

The study will include the following evaluations of safety and tolerability according to the time points provided in the Schedule of Activities in Section 1.2.

The sponsor will use the safety assessments, including clinical laboratory tests, from Week 32 in Study TRD3013 in the database for Day 1 in this long-term extension study; these procedures do not need to be repeated for participants who return for esketamine nasal spray dosing within 14 days after the Week 32 visit in TRD3013.

CONFIDENTIAL – FOIA Exemptions Apply in U.S.

8.2.1. **Physical Examinations**

Body Weight

Body weight will be measured as per the Schedule of Activities.

Nasal Examinations

Nasal examinations (including the upper respiratory tract/throat) will be conducted by a qualified healthcare practitioner authorized by local regulation to conduct a physical examination. The objective of the examination is to rule out any participants with medical conditions that may impede drug delivery or absorption. Abnormalities noted during the nasal examination will be reported as adverse events.

The nasal examination consists of a visual inspection of the nostrils, nasal mucosa, and throat for nasal erythema, rhinorrhea, rhinitis, capillary/blood vessel disruption, and epistaxis, and will be graded as follows: absent, mild, moderate, or severe.

8.2.2. Vital Signs

Pulse/heart rate, respiratory rate, and blood pressure will be assessed.

Blood pressure and pulse/heart rate measurements will be assessed supine with a completely automated device or using manual techniques.

Blood pressure and pulse/heart rate measurements should be preceded by at least 5 minutes of rest in a quiet setting without distractions (eg, television, cell phones).

8.2.3. **Clinical Safety Laboratory Assessments**

Blood samples for serum chemistry and hematology and a random urine sample for urinalysis will be collected at the time points identified in the Schedule of Activities and as noted in Appendix 8, Clinical Laboratory Tests. Participants should fast for at least 8 hours prior to visits when blood samples will be collected. The investigator must review the laboratory results, document this review, and record any clinically relevant changes occurring during the study in the AE section of the eCRF. The laboratory reports must be filed with the source documents.

8.2.4. **Pregnancy Testing**

A negative urine pregnancy test must be obtained before the first dose of study intervention on Day 1. Additional serum or urine pregnancy tests may be performed, as determined necessary by the investigator or required by local regulation, to establish the absence of pregnancy at any time during the participation in the study and

- every 4 weeks.
- at end of study intervention.
- at 2 weeks after the last dose of study intervention.

8.2.5. Suicidal Ideation and Behavior Risk Monitoring

Esketamine nasal spray is considered to be an antidepressant. There has been some concern that antidepressants may be associated with an increased risk of suicidal ideation or behavior when given to some participants with MDD. Although esketamine nasal spray or other similar treatments for MDD have not been shown to be associated with an increased risk of suicidal thinking or

CONFIDENTIAL - FOIA Exemptions Apply in U.S.

behavior when given to this participant population, the sponsor considers it important to monitor for such events before or during this clinical study.

Participants being treated with esketamine nasal spray and an SSRI/SNRI should be monitored appropriately and observed closely for suicidal ideation and behavior or any other unusual changes in behavior. Consideration should be given to discontinuing esketamine nasal spray and/or the SSRI/SNRI in participants who experience signs of suicidal ideation or behavior.

If the participant agrees, the investigator can request that families and caregivers of participants being treated with study intervention monitor participants for the emergence of unusual changes in behavior, as well as the emergence of suicidal ideation and behavior, and to report such symptoms immediately to the study investigator.

Intervention-emergent suicidal ideation and behavior will be assessed during the study using the C-SSRS. If early signs of suicidal ideation are identified then the C-SSRS should be applied more frequently than the time points listed in the Schedule of Activities, at the discretion of the investigator.

The C-SSRS is a low-burden measure of the spectrum of suicidal ideation and behavior that was developed in the National Institute of Mental Health Treatment of Adolescent Suicide Attempters Study to assess severity and track suicidal events through any treatment (Posner 2011). It is a clinical interview which supports suicide risk assessment through a series of simple, plain-language questions. It identifies risk not only if someone has previously attempted suicide, but also if he or she has considered suicide, prepared for an attempt (for example, buying a gun, collecting pills, or writing a suicide note), or aborted plans for suicide because of a last-minute change of heart or a friend's intervention. Users of the C-SSRS tool ask people:

- Whether and when they have thought about suicide (ideation)
- What actions they have taken and when to prepare for suicide
- Whether and when they attempted suicide or began a suicide attempt that was either interrupted by another person or stopped of their own volition.

8.3. Adverse Events, Serious Adverse Events, and Other Safety Reporting

Timely, accurate, and complete reporting and analysis of safety information, including adverse events, serious adverse events, and PQC, from clinical studies are crucial for the protection of participants, investigators, and the sponsor, and are mandated by regulatory agencies worldwide. The sponsor has established Standard Operating Procedures in conformity with regulatory requirements worldwide to ensure appropriate reporting of safety information; all clinical studies conducted by the sponsor or its affiliates will be conducted in accordance with those procedures.

Adverse events will be reported by the participant (or, when appropriate, by a caregiver, surrogate, or the participant's legally acceptable representative) for the duration of the study.

For study intervention that meets the definition of a combination product, malfunctions or deficiencies of a device constituent will be reported as PQC.

Further details on adverse events, serious adverse events, and PQC can be found in Appendix 5, Adverse Events, Serious Adverse Events, Product Quality Complaints, and Other Safety Reporting: Definitions and Procedures for Recording, Evaluating, Follow-Up, and Reporting.

8.3.1. Time Period and Frequency for Collecting Adverse Event and Serious Adverse Event Information

All Adverse Events

All adverse events and special reporting situations, whether serious or non-serious, will be reported from Day 1, starting after the first dose of esketamine nasal spray, until completion of the participant's 2-week safety follow-up visit. Prior to the first dose in this long-term extension, this information will be captured as part of Study TRD3013.

Serious Adverse Events

All serious adverse events, as well as PQC, occurring during the study must be reported to the appropriate sponsor contact person by study-site personnel within 24 hours of their knowledge of the event.

Serious adverse events, including those spontaneously reported to the investigator within 30 days after the last dose of study intervention, must be reported. The sponsor will evaluate any safety information that is spontaneously reported by an investigator beyond the time frame specified in the protocol.

Information regarding serious adverse events will be transmitted to the sponsor using the Serious Adverse Event Form, which must be completed and signed by a physician from the study site, and transmitted to the sponsor within 24 hours. The initial and follow-up reports of a serious adverse event should be made by facsimile (fax). Telephone reporting should be the exception and the reporter should be asked to complete the appropriate form(s) first.

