1.3. Schedule of Activities (SoA)

			Long-term I	Extension Phase		
		ESK Dosing:			Week 104/	
		Once Weekly			End-of-Study b,c,d/	
		or Every	Every	Every	Early Study	Safety follow-up
	Day 1 ^a	2 Weeks	4 Weeks	24 Weeks	Withdrawal Visite	visit ^f
Visit Window (Days)	+14	±3	±3	±3	±3	±2
Administrative Procedures						
Informed consent	Xg					
Inclusion/exclusion criteria	X					
Patient-reported outcomesh						
PHQ-9			X		X	
EQ-5D-5L			X		X	
Clinician-rated scales and questionnairesi						
MADRS: efficacy assessment			\mathbf{X}^{j}		X	
CGI-S			X		X	
C-SSRS (Since Last Visit version)			X		X	
Safety assessments						
Hematology/chemistry, urinalysis (local)k				X	X	X
Pregnancy testing ¹			X		X	X
Body weight					X	
Nasal examination predose ^m	X	X			X ⁿ	
Vital signs predose ^o	X	X			X ⁿ	
Vital signs postdose ^{o,p}	X	X			X ⁿ	
Vital signs ^{o,q}					Xr	X
Study intervention procedures						
Nasal treatment sessions ^{s,t}	X	X ^u			X ^c	
Drug accountability: esketamine	X	X			X ^c	
Medication compliance counseling (SSRI/SNRI) ^v	X	X				
Ongoing						
Concomitant therapy/psychotherapy	X	X			X	X
Adverse events	X	X			X	X

Abbreviations: C-SSRS=Columbia-Suicide Severity Rating Scale; CGI-S= Clinical Global Impression – Severity; eCRF=electronic case report form; EQ-5D-5L=European Quality of Life Group, 5 dimension, 5-level (questionnaire); MADRS=Montgomery-Asberg Depression Rating Scale; MDD=major depressive disorder; PHQ-9=Patient Health Questionnaire – 9; PRO=patient-reported outcome; SmPC=Summary of Product Characteristics; SNRI=serotonin-norepinephrine reuptake inhibitor; SSRI=selective serotonin reuptake inhibitor.

- Day 1 **should** be the same day as Week 32 visit from Study TRD3013. If a participant cannot receive the esketamine nasal spray dose on the same day as the Week 32 visit in Study TRD3013, the participant may be enrolled in this study (TRD4010) as long as they continue their current SSRI/SNRI and receive their first dose of esketamine nasal spray within 14 days of the Study TRD3013 Week 32 visit date; Day 1 of this study will be the day of the esketamine nasal spray dose. The sponsor will use the PROs, clinician-rated scales, and safety assessments, including clinical laboratory tests, from Week 32 in Study TRD3013 in the database for Day 1 in this study; these procedures do not need to be repeated for participants who return for esketamine nasal spray dosing within 14 days after the Week 32 visit in TRD3013.

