- O Vital signs: blood pressure, pulse/heart rate, respiratory rate.
- P Vital signs will be measured at approximately 40 minutes after esketamine nasal spray dose and subsequently as clinically warranted until blood pressure values decline. Participants must be monitored by a healthcare professional until the participant is considered clinically stable and ready to leave the study site. If blood pressure remains elevated for a prolonged period of time, assistance should promptly be sought from practitioners experienced in blood pressure management. Participants who experience symptoms of a hypertensive crisis should be referred immediately for emergency care.
- ^q At an early study withdrawal visit or the safety follow-up visit (no esketamine nasal spray dose), vital signs will be performed according to usual practice.
- Vital signs performed for participants not administrating esketamine nasal spray at this visit.
- If the participant has nasal congestion on the dosing day, a nasal decongestant can be used to reduce congestion (but not within 1 hour before esketamine dosing) or the dosing day can be delayed (per the permitted visit window).

- ^t Esketamine nasal spray dosing and related safety-monitoring procedures MUST be performed LAST at all visits. Esketamine nasal spray must NOT be administered before all other visit assessments are completed.
- ^u The frequency of nasal treatment sessions may be individualized on even week visits from once weekly to every 2 weeks based on severity of depressive symptoms and at the discretion of the investigator. If participants show early signs of worsening of depressive symptoms after reduced treatment frequency, the treatment frequency can be changed back to once weekly at any visit.

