5.3.2.1. Analysis Methods

5.3.2.1.1. Primary Analysis

The verbatim terms used in the case report form by investigators to identify AEs will be coded using the Medical Dictionary for Regulatory Activities (MedDRA). Any AE occurring at or after the initial administration of study intervention in Study 54315419TRD3013 through completion the participant's 2-week safety follow-up visit in Study 54135419TRD4010 is considered to be treatment emergent. Serious AEs reported within 30 days after the last dose of study intervention in Study 54135419TRD4010 are also regarded as treatment emergent. If the event occurs on the day of the initial administration of study intervention, and either event time or time of administration are missing, then the event will be assumed to be treatment emergent. If the event date is recorded as partial or completely missing, then the event will be considered to be treatment emergent unless it is known to be prior to the first administration of study intervention based on partial onset date or resolution date. All reported treatment-emergent AEs will be included in the analysis. For each AE, the number, proportion and incidence rate of participants who experience at least 1 occurrence of the given event will be summarized. The incidence rate is defined as the numbers of participants who experience at least 1 occurrence of the AE divided by the time at risk. Time at risk is defined as time from initial administration of study intervention in Study 54135419TRD3013 until first occurrence of AE or until last dose of study intervention plus 30 days (if participant did not experience AE). To calculate time at risk if the start date of an AE is missing completely or partially, following imputation rule will be applied:

If the onset date of an adverse event is missing day only, it will be set to:

- i) First day of the month that the AE occurred, if month/year of the onset of AE is different than the month/year of initial dosing date of Study 54135419TRD3013
- ii) The day of initial dosing in Study 54135419TRD3013, if the month/year of the onset of AE is the same as month/year of the initial dose date and month/year of the AE resolution date is different
- iii) The day of initial dosing in Study 54135419TRD3013 or day of AE resolution date, whichever is earliest, if month/year of the onset of AE and month/year of the initial dosing date of Study 54135419TRD3013 and month/year of the AE resolution date are the same.

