5.3.2.1.3. Supplementary Analysis

Several supplementary analyses will be performed where a selection of AEs will be included

- Only including AEs starting at or after the initial administration of study intervention in Study 54135419TRD3013 and before the day of first dose in Study 54135419TRD4010
- Only including AEs starting at or after the initial administration of study intervention in Study 54135419TRD4010 through the day of last dose in Study 54135419TRD4010 plus 30 days. Following outputs will be repeated:
 - o Overall summary of TEAE
 - TEAE by SOC and PT
 - o TEAE by maximum severity
 - o TEAE by maximum relationship to esketamine

- o Treatment-emergent SAE
- o TEAE of special interest
- o TEAE leading to esketamine dose interruption or change
- o TEAE stratified by AE duration (end date same as start date versus end date later than start date)
- o Summary of days with TEAE
- o Proportion of TEAEs occurring on dosing days
- o Proportion of TEAEs which occur on dosing days with same day resolution
- Only including AEs starting at or after the initial administration of study intervention in Study 54135419TRD3013 through the day on which there is a switch of SSRI/SNRI or the day of last dose in Study 54135419TRD4010 plus 30 days, whichever comes first
- Only including AEs starting at or after the initial administration of study intervention in Study 54135419TRD4010 through the day on which there is a switch of SSRI/SNRI or the day of last dose in Study 54135419TRD4010 plus 30 days, whichever comes first

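### AEs that start on extension Day 1 before the dose fall in neither of the two by-period supplementary AE analyses

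*Protocol*

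**What the plan says.** **Collection rule.** Under Protocol 8.3.1, AEs in the extension "will be reported from Day 1, starting after the first dose of esketamine nasal spray". For anything earlier the same section says: "Prior to the first dose in this long-term extension, this information will be captured as part of Study TRD3013". The dividing point is therefore the dose, not the date.

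**By-period analyses.** SAP 5.3.2.1.3 lists supplementary analyses that each take a subset of AEs, selected by when the AE starts. The TRD3013-period set begins at the first parent-study administration and covers onsets "before the day of first dose in Study 54135419TRD4010". The TRD4010-period set is worded "Only including AEs starting at or after the initial administration of study intervention in Study 54135419TRD4010 through the day of last dose", with 30 days added at the end. The second of the two SSRI/SNRI-switch analyses in that section has the same TRD4010 start.

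**Primary analysis.** SAP 5.3.2.1.1 uses one unbroken window: "Any AE occurring at or after the initial administration of study intervention in Study 54315419TRD3013 through completion the participant's 2-week safety follow-up visit" in TRD4010 (parent study number as printed). SAEs within 30 days of the last dose are added.

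**Day 1.** The Schedule of Activities (Protocol 1.3, footnote a) says Day 1 should "be the same day as Week 32 visit from Study TRD3013", with a delay of up to 14 days allowed. On the order of events within a visit it states: "Esketamine nasal spray must NOT be administered before all other visit assessments are completed".

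**The concern.** One window closes on a calendar date and the next opens at a clock time. Whatever starts between the beginning of Day 1 and the dose lies between them. The protocol gives that interval to TRD3013, so the events are collected as parent-study events and then excluded by the SAP's own parent-period window.

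The interval falls on a day with many assessments. Nasal examination and vital signs are scheduled before the Day 1 dose, and Protocol 8.2.1 makes nasal abnormalities reportable as AEs. Week 32 laboratory results stand in for Day 1 values. Clinically relevant laboratory changes are recorded as AEs, and SAP 5.6.3.1 reports laboratory abnormalities only through the AE analysis. If the onset of such a finding is dated to that day before the dose, it appears in neither by-period table.

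At stake is the separation of parent-study AEs from extension AEs. Among the SAP's AE analyses, these two are meant to divide the combined experience at the start of the extension, and the TRD4010 set repeats the main outputs, including SAEs and AEs of special interest.

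**Working it through.** The plan gives no figure to reproduce. The check is whether each onset time belongs to a window.

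**Definitions.** Let *t* be the AE onset, *a* the first TRD3013 administration, *d* the date and time of the first TRD4010 administration, and *L* the last TRD4010 dose.

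- Primary (SAP 5.3.2.1.1), at its start: *t* ≥ *a*, with no break at *d*.
- TRD3013 period (SAP 5.3.2.1.3): *t* ≥ *a* and date(*t*) < date(*d*).
- TRD4010 period (SAP 5.3.2.1.3): *d* ≤ *t* ≤ *L* + 30 days.

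**The gap.** An onset is in neither period when date(*t*) = date(*d*) and *t* < *d*, that is, on Day 1 before the dose. For the same *t*, Protocol 8.3.1 assigns the event to TRD3013.

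**Test cases** (illustrative clock times, dose at 11:00):

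| AE onset | Primary | TRD3013 period | TRD4010 period | Periods containing it |
|---|---|---|---|---|
| *Day 1 on the Week 32 visit day* | | | | |
| 3 days before Week 32, found at the visit | yes | yes | no | 1 |
| Day 1 (= Week 32 visit day), 09:00 | yes | no | no | **0** |
| Day 1, 11:00, at the dose | yes | no | yes | 1 |
| Day 1, 12:00, after the dose | yes | no | yes | 1 |
| *Day 1 seven days after Week 32* | | | | |
| 3 days before Week 32, found at the visit | yes | yes | no | 1 |
| Week 32 visit day, 09:00 | yes | yes | no | 1 |
| Day 1, 09:00, before the dose | yes | no | no | **0** |
| Day 1, 11:00, at the dose | yes | no | yes | 1 |
| Day 1, 12:00, after the dose | yes | no | yes | 1 |

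**After the change.** Replace the TRD3013 condition with *a* ≤ *t* < *d*. Both rows showing 0 become 1, in the TRD3013 period. Every other row stays at 1, so the windows adjoin without overlap.

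**Extent of the interval.** It is part of one day per participant. Combined follow-up is up to 32 + 104 = 136 weeks, or 136 × 7 = 952 days, of which the parent study is 32 × 7 = 224 days. With the expected 100 to 200 participants there are 100 to 200 such part-days. The documents give no AE rate for them, so no event count follows.

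**Missing times.** SAP 5.3.2.1.1 counts an AE on the day of initial administration as treatment emergent if its time or the dose time is missing. The surrounding text fixes that administration as the first one in TRD3013. The SAP does not say whether the rule carries over to the TRD4010 start. If it does, untimed Day 1 AEs go to the TRD4010 period; if it does not, their allocation is undefined. In either case, an AE with a known time before the dose is not rescued.

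**The case against.** The strongest reply is that almost nothing is affected. The primary endpoint is intact and only supplementary outputs change. Entrants were last dosed at Week 30 or 31 of TRD3013, and Protocol 2.2.3.4 reports that most AEs arise after dosing on the dosing day and resolve the same day. Sedation and dissociation are therefore unlikely to start in this interval. The parent study also has its own clinical study report, cited in the SAP but not available here, so these tables need not be the only account of parent-period AEs. All of this stands, and it limits the size of the point. It does not make the windows meet.

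The missing-time rule could also be read as applying to the TRD4010 start. That is a natural reading, but it is unstated and concerns only untimed events.

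A reader might infer two stronger claims:

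- **That AEs found at the parent study's final visit are dropped as a group.** The documents do not support this. Selection is by onset, and no section dates an AE to the visit at which it was detected. An AE found at Week 32 that began earlier counts in the TRD3013 period. So does one starting on the Week 32 visit day when Day 1 comes later.
- **That, with correct windows, the two by-period tables should sum to the pooled table.** They would not. SAP 5.3.2.1.1 counts participants with at least one occurrence and divides by time at risk. A participant with the same AE in both periods counts once when pooled and once in each period. The far ends also differ on paper: the 2-week follow-up visit plus SAEs to 30 days in the primary analysis, against last dose plus 30 days in the TRD4010 set.

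**Conclusion.** The point holds as a boundary error in SAP 5.3.2.1.3. AEs with onset on extension Day 1 before the dose are left out of both by-period analyses, although Protocol 8.3.1 assigns them to TRD3013. Nothing else in the two documents closes the gap. Protocol 8.3.1 is the rule the SAP window fails to match and is not itself at fault on this point.

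The effect is confined to these supplementary analyses. The TRD4010-start switch analysis also leaves these events out, which agrees with the protocol's allocation, so it needs no change.

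The conclusion rests on reading the SAP literally, as a date cut followed by a time cut. That the number of affected events is small is a judgement from the short interval and the usual timing of AEs, not a calculation. This is a minor wording correction.

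**What to change.** 1. In SAP 5.3.2.1.3, end the TRD3013-period window strictly before the date and time of the first TRD4010 administration, replacing the cut at the start of that day.
2. Add a tie-break: a Day 1 AE with a missing event time or dose time goes to the study in which it was recorded. State that this replaces the missing-time rule of SAP 5.3.2.1.1 at this boundary. Recording should follow Protocol 8.3.1. The general note in Protocol 10.5.1 that AE collection starts at consent should be read with that in mind.
3. Check at event level that each AE from the first TRD3013 dose onward falls in exactly one of the two periods at this boundary. Do not test whether participant counts or incidence rates sum to the pooled analysis.

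The cost is one phrase, one tie-break sentence and one programming condition. Data collection and the primary analysis do not change.
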